concentration of dexamethasone from DexNP treatment was still 10-times higher than what was observed with Maxidex® treatment. These results demonstrate that dexamethasone, complexed with CD nanoparticles, elicits a higher concentration and longer duration of action in the tear fluid than the currently available product, Maxidex®. Importantly, DexNP was well tolerated by the subjects and no serious adverse events (SAEs) were observed.

A study conducted by Saari et al. ([Saari, Nelimarkka et al. 2006](#)) evaluated the efficacy of an eye drop containing 0.7% dexamethasone-CD suspension, applied once daily, compared to a 0.1% dexamethasone sodium phosphate eye drops, applied three times daily for the treatment of post-operative inflammation after cataract surgery. The dexamethasone-CD suspension was shown to be safe and more effective in treating post-operative inflammation, after once daily dosing, than 0.1% dexamethasone sodium phosphate eye drops applied three times daily.

In the human studies with DexNP to date, DexNP was well tolerated and the only AE reported has been a modest rise in intraocular pressure (IOP), a known side effect of dexamethasone use, which subsided following discontinuation of DexNP in all cases ([Kristinsson, Fridriksdottir et al. 1996](#)) ([Johannesson, Moya-Ortega et al. 2014](#)) ([Saari, Nelimarkka et al. 2006](#)) ([Tanito, Hara et al. 2011](#)) ([Ohira, Hara et al. 2015](#)) ([Krag and Hessellund 2014](#)) ([Shulman, Johannesson et al. 2015](#)).

Building on the enhanced ocular penetration of DexNP, as well as its favorable efficacy results and safety profile, Oculis has developed an updated formulation, OCS-01, consisting of water soluble 1.5% Dexamethasone- γ CD complexes to treat post-surgical inflammation.

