7.2 Safety Measures

Safety will be assessed by the following measures:

- Change from baseline of pin-hole VA (without any other correction) as measured on the ETDRS chart
- Change from baseline of IOP
- AE rates

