9.4.2 Unscheduled Visits

In the case of an AE, an unscheduled visit may occur. The Investigator may perform additional assessments at their discretion. All additional assessments will be documented in the subject's source document and eCRF.

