8.2.3 MISSING SAFETY DATA

For all safety variables, missing data will not be imputed, observed values will be presented.

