8.4 Data Analysis Conventions

All data analysis will be performed by SDC after the study is completed and the database has been locked. After the study database has been locked and any other prerequisites for unmasking are met (e.g. all protocol deviations have been classified as major or minor), unmasking will be done for the purpose of the primary analysis, and all planned tables, listings, and figures (TLF) will be generated.

Statistical programming and analyses will be performed using SAS® version 9.4 or higher. Output will be provided in rich text format (RTF) for tables and portable document format (PDF) for TLF using landscape orientation. All study data will be listed by subject, treatment, and visit (as applicable) based on all randomized subjects unless otherwise specified (e.g. demography data, which is also captured for screen failure subjects).

Summaries for continuous and ordinal variables will include the number of observations (n), arithmetic mean, standard deviation (SD), median, minimum, and maximum. Minima and maxima will be reported with the same precision as the raw values; means and medians will be presented to one additional decimal place than reported in the raw values. Standard deviations will be presented to two additional decimal places than reported in the raw values. Summaries for discrete variables will include counts and percentages. All percentages will be rounded to one decimal place (i.e. XX.X%). Differences between active treatment groups and placebo (vehicle) will be calculated as active minus placebo and change from baseline will be calculated as follow-up visit minus baseline.

Dates within subject data listings will be presented based on ISO 8601 standard, as DD-MMM-YYYY.

All efficacy analyses will use a [REDACTED]

[REDACTED]

[REDACTED]

[REDACTED]

Unless otherwise specified, summaries will be presented by treatment group and (where applicable) eye and visit. Analysis by visit will be based on nominal visit identifier. Data from unscheduled visits, unscheduled time points, or unplanned repeat assessments will be included in the data listings. In general, these data will be excluded from the summary tables unless otherwise specified.

Efficacy summaries by treatment group will include the 3 protocol defined treatment groups. Summaries of subject disposition and baseline characteristics will include additional subject groupings defined as:

■ [REDACTED]

■ [REDACTED]

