14.5 Intraocular Pressure (IOP)

Subjects' IOP will be assessed in each eye [REDACTED]

■ [REDACTED]
■ [REDACTED]

[REDACTED]

[REDACTED]

[REDACTED]

[REDACTED]

[REDACTED]

Analyses of concomitant IOP lowering medications is described previously, within Section 11.2.

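### By default the SAP keeps unscheduled IOP readings out of summary tables, so a peak managed between visits may not be summarised by arm

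*SAP*

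**What the plan says.** SAP 8.4 sets three conventions that act together. On visits: "Analysis by visit will be based on nominal visit identifier". On extra readings: "Data from unscheduled visits, unscheduled time points, or unplanned repeat assessments will be included in the data listings". On tables: "In general, these data will be excluded from the summary tables unless otherwise specified". SAP 8.2.3 adds: "For all safety variables, missing data will not be imputed, observed values will be presented".

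Protocol 9.4.2 explains how extra readings arise: "In the case of an AE, an unscheduled visit may occur. The Investigator may perform additional assessments at their discretion". It requires them to be entered in the eCRF.

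Protocol 7.2 names "Change from baseline of IOP" as a safety measure, next to change in pin-hole visual acuity (VA) and adverse event rates. Protocol 3.1 says that in human DexNP studies so far "the only AE reported has been a modest rise in intraocular pressure (IOP), a known side effect of dexamethasone use", and that it subsided in every case once DexNP was stopped.

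In SAP 14.5 the readable text is little more than "IOP will be assessed in each eye" and a cross-reference to SAP 11.2 for IOP-lowering medication. The rest is blacked out. SAP 14.2 on VA shows only its opening words, and most of protocol 11.6 is also redacted.

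**The concern.** A rule that leaves extra readings out of tables does little harm when those readings are routine. Here the one stated reason for an unscheduled visit is an adverse event, so the readings left out include those taken because something was wrong.

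IOP is the measure most exposed. The protocol describes the rise as reversible. Subjects who stop study drug stay in the study and attend later visits (protocol 6.6), and non-prostaglandin IOP-lowering agents are allowed (exclusion criterion 7). A rise can therefore be found, managed and gone by the next scheduled reading. The by-visit table would then show the recovered value and not the peak. The same holds for a VA loss seen only at an adverse event visit.

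At stake is whether the report gives, by arm, the size of the worst IOP values and the number of subjects who crossed any threshold the sponsor uses.

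**Working it through.** The plan states no figure on this point, so there is none to reproduce. The check is a reading of the rules side by side, with arithmetic on visit windows and arm size.

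**Scheduled IOP readings.** Protocol 9.3 lists no IOP at Visit 2. After first dose, IOP is measured at Visits 4 to 7, whose windows are Days 3–5 (4 ± 1), 7–9 (8 ± 1), 13–17 (15 ± 2) and 20–24 (22 ± 2).

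Shortest gap = earliest day of the later visit minus latest day of the earlier visit. Longest gap = latest minus earliest.

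| Interval | Nominal | Shortest | Longest |
|---|---|---|---|
| Visit 4 to 5 | 8 − 4 = 4 days | 7 − 5 = 2 | 9 − 3 = 6 |
| Visit 5 to 6 | 15 − 8 = 7 days | 13 − 9 = 4 | 17 − 7 = 10 |
| Visit 6 to 7 | 22 − 15 = 7 days | 20 − 17 = 3 | 24 − 13 = 11 |

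SAP 3.1 gives 14 days of dosing. If these start on Day 1, the last dose is on Day 14, so only Visits 4 and 5 are certain to fall within planned dosing. Visit 6 may fall from Day 13 to Day 17, that is, up to 17 − 14 = 3 days after the last dose. There is room for a rise to appear and be managed between scheduled readings. These gaps only show that the situation can arise. A rise that prompts no visit leaves no reading to exclude.

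**Tracing one case.** Suppose a subject is seen on Day 11 for an adverse event, has a high IOP, and has a normal IOP at Visit 6.

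| Output | What it would show |
|---|---|
| IOP table by nominal visit (SAP 8.4 default) | Visits 5 and 6 only; the Day 11 value is left out |
| Treatment-emergent adverse event tables (SAP 14.1) | The event, by arm, preferred term and maximum severity, if recorded as an adverse event; no mmHg |
| IOP-lowering medication listing (SAP 11.2) | The treatment, if one was given; no mmHg |
| Data listings (SAP 8.4) | The Day 11 value, for that subject only |

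No readable output both gives the pressure and summarises it by arm.

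**Effect on a summary.** For one subject, the maximum over all readings cannot be lower than the maximum over scheduled readings. So a count of subjects crossing an upper threshold, taken from scheduled readings only, can equal or understate the count from all readings within an arm.

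Each subject whose only crossing was at an unscheduled reading changes the arm's proportion by 1/n. The total is about 150 (protocol 6.1), and the allocation ratio is redacted.

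- Assumed equal split, n = 150/3 = 50: 1/50 = 2.0 points.
- n = 60: 1/60 = 1.7 points.
- n = 30: 1/30 = 3.3 points.

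How many such subjects there would be cannot be derived from the documents.

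**The case against.** The strongest reply is that the rule is only a default. It opens with a qualifier and allows exceptions, and the natural places for an exception, SAP 14.5 and 14.2, are almost wholly blacked out. This stands. A reader might infer that the plan has no worst-value IOP summary, or that an unscheduled peak never reaches the IOP summary. The documents support neither, because redacted text cannot be counted as absent.

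The second reply is that the event is not lost. An IOP rise recorded as an adverse event enters the ocular adverse event tables by arm, any IOP-lowering treatment is flagged and listed, and the reading itself is listed. This also stands. What those outputs lack is the pressure summarised by arm, and the first of them depends on the investigator recording an adverse event.

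The third reply is that no bias between arms has been shown. A reader might infer that leaving out these readings pulls the comparison of active arms with vehicle towards no difference. The understatement within an arm is a matter of arithmetic, but its split between arms is unknown. Unscheduled visits may follow any adverse event in any arm, and IOP need not be measured at them. The objection holds.

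The last reply is that a maximum over all readings favours subjects with few visits: more readings give more chances of an extreme value. This is a real drawback, and the fix has to deal with it.

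**Conclusion.** The point stands as a cheap improvement to a default, not as an error in the plan. On the readable text, IOP and VA readings from unscheduled visits and unplanned repeats are left out of summary tables, and nothing readable makes an exception for a worst value or a threshold count. A peak managed between visits would then be visible as an event and in a listing, but its size would not be summarised by arm.

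Each affected subject is 2.0 percentage points of an arm of 50, or 1.7 to 3.3 points for arms of 60 down to 30. This assumes the arm size and that the subject's only crossing was at an unscheduled reading. The number of affected subjects is unknown.

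Two further inferences go too far. The IOP comparison cannot be said to bear on the choice between once and twice daily dosing: the secondary objective (protocol 4.1, SAP 2) concerns optimal frequency for treating inflammation and pain. Nor can IOP rise be called the product's one known risk. Protocol 3.1 reports it as the only adverse event in DexNP studies to date, calls it modest, and describes OCS-01 as an updated formulation.

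**What to change.** The sponsor, who can read SAP 14.5 and 14.2 in full, should first check whether they already make this exception. If they do not, add one sentence to SAP 8.4: for IOP and VA, the per-subject worst post-baseline value, the largest change from baseline and any threshold-crossing count use all readings after first dose, including those from unscheduled visits and unplanned repeats. By-visit summaries stay on nominal scheduled visits.

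Because the number of readings will differ between subjects, show the number of readings per subject by arm, or give a scheduled-only version of the same summary alongside.

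The cost is SAP wording and one extra row or table. No new data are needed, since protocol 9.4.2 already requires the extra assessments in the eCRF. The reported figures may look slightly less favourable.

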8.5 Adjustments for Multiplicity

The hierarchy of statistical hypotheses for testing is described in Section 2.5.

[REDACTED]

9. Disposition of Subjects

Disposition of subjects will be summarized for the [REDACTED]

[REDACTED]

[REDACTED]

[REDACTED]

[REDACTED]

Disposition of subjects will also be summarized among [REDACTED]

[REDACTED]

[REDACTED]

The number and percentage of subjects with major protocol deviations will be summarized by [REDACTED]

[REDACTED]

[REDACTED]

[REDACTED]

[REDACTED]

[REDACTED]

[REDACTED]

In addition, subject listings will be provided that include informed consent date, inclusion and exclusion criteria violations, and exclusions from the PP population.

Details of the study randomization, including randomization date and time, randomized treatment and actual treatment, will also be included within a subject listing.

10. Demographic and Pretreatment Variables

The demographic variables collected in this study include [REDACTED]

[REDACTED]

[REDACTED]

[REDACTED]

Age (years) will be summarized, overall and by treatment, using [REDACTED]

[REDACTED]

[REDACTED]

[REDACTED]

A subject listing that includes all demographic variables will be provided.

11. Medical History and Concomitant Medications

11.1 Medical History

Medical history and ocular history will be summarized [REDACTED]

[REDACTED]

[REDACTED]

Medical history and ocular history will be coded using Medical Dictionary for Regulatory Activities (MedDRA), version 22.0 (or higher).

Non-ocular medical history will be summarized [REDACTED]

[REDACTED]

[REDACTED]

[REDACTED]

[REDACTED]

[REDACTED]

Within table summaries, SOC will be listed in ascending alphabetical order; PTs will be listed in order of descending frequency for all subjects within each SOC.

Listings of medical history will be generated separately for ocular and non-ocular data. The study eye will be identified within listings of ocular medical history.

Details of each subject's cataract surgery will also listed.

11.2 Prior and Concomitant Medications

Prior and concomitant medication usage will be summarized with the [REDACTED]

Prior and concomitant medications will be coded using World Health Organization (WHO) Drug Global (B3, March 2019 [or higher]) dictionary, and summarized to the therapeutic drug class (Anatomical Therapeutic Chemical [ATC] Level 4 classification) and preferred name. If the ATC Level 4 classification is not provided, the next lowest classification that is provided in the coding dictionary will be used. The preferred name will be defined as the active ingredient; if the active ingredient is not provided or includes more than two ingredients (e.g. multivitamins), then the drug name will be summarized as the preferred name. Any uncoded terms will be summarized under the ATC classification and preferred name of "Uncoded."

Prior medications are defined as [REDACTED]

[REDACTED] Concomitant medications are defined as [REDACTED]

[REDACTED]

[REDACTED]

[REDACTED]

Ocular medications are a subset of the overall medications and consist of those medication records where the location field on the eCRF is marked as OD, OS, or OU. In addition, medications which are classified as 'non-ocular' on the eCRF but which have potential to impact anterior chamber cell count or ocular pain will be reclassified as an ocular medication for analysis. These medications will be identified via manual review of coded medication classes as well as review of the indication fields. For purposes of analysis, the eye location value for analysis will be defined as OU.

IOP lowering medications are a subset of medications where the investigator has indicated on the eCRF that the medication was used to lower IOP. Concomitant medications will be summarized separately for ocular and non-ocular medications. [REDACTED]

[REDACTED] Medications reported as OU will be summarized as a medication for both the study eye as well as the non-study eye.

[REDACTED]

[REDACTED]

[REDACTED]

[REDACTED]

[REDACTED]

Listings of prior and concomitant medications will be generated separately for ocular and non-ocular data. A separate listing will be generated for IOP lowering medications.

Rescue medication usage is an efficacy measure for this study, analysis of rescue medication is described separately in Section 13.2.5.

12. Dosing Compliance and Treatment Exposure

12.1 Dosing Compliance

Details of individual administrations of study medication done at home by subjects are not captured within the clinical database, therefore dosing compliance will not be summarized.

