8 STUDY MATERIALS

8.1 Study Treatment(s)

8.1.1 Study treatment(s)

- OCS-01 ophthalmic suspension (QD) + Placebo (vehicle) (QD)
- OCS-01 ophthalmic suspension (BID)
- Placebo (vehicle) ophthalmic suspension (BID)

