9.3 Examination Procedures

Procedures to be performed at each study visit with regard to the study objectives are detailed in [Appendix 2: Examination Procedures, Tests, Equipment, and Techniques](#).

Visit 1 — Screening and Baseline Evaluations (-28 to -1 days prior to surgery)

- Informed consent/assent
- Demographic data
- Medical and medication history
 - Current underlying conditions, including those that began within the last 30 days, which may have been resolved before Visit 1 (Day -1 to Day -28 [prior to surgery]), must be recorded.
 - Any medications the subject is taking, as well as those the subject may have taken but discontinued within 30 days prior to Visit 1 (Day -1 to Day -28 [prior to surgery]) must be recorded.
- Urine pregnancy test (if applicable)
- Inclusion/exclusion criteria
- Ocular pain (study eye only)
- Pin-hole VA
- Slit lamp biomicroscopy

- Ocular inflammation assessment of the anterior chamber cell and flare (study eye only)
- IOP
- Dilated indirect ophthalmoscopy

Visit 2 — Day 1 (18 to 30 hours post-surgery)

- Review inclusion/exclusion criteria
- Medical and medications update
- Ocular pain (study eye only)
- Pin-hole VA
- Slit lamp biomicroscopy
- Ocular inflammation assessment of the anterior chamber cell and flare (study eye only)
- Randomization
- Dose and dispense study medication and dosing diary
- Query for AEs

Visit 3 — Day 2 (Telephone Call)

- Ocular pain (study eye only)

Visit 4 — Day 4 (\pm 1 day window)

- Medical and medications update
- Ocular pain (study eye only)
- Pin-hole VA
- Slit Lamp Biomicroscopy
- Ocular inflammation assessment of the anterior chamber cell and flare (study eye only)
- IOP
- Query for AE

Visit 5 — Day 8 (\pm 1 day window)

- Medical and medications update
- Ocular pain (study eye only)
- Pin-hole VA
- Slit lamp biomicroscopy
- Ocular inflammation assessment of the anterior chamber cell and flare (study eye only)

- IOP
- Query for AEs

Visit 6 — Day 15 (± 2 day window)

- Medical and medications update
- Ocular pain (study eye only)
- Pin-hole VA
- Slit lamp biomicroscopy
- Ocular inflammation assessment of the anterior chamber cell and flare (study eye only)
- IOP
- Query for AEs

Visit 7 — Day 22 (± 2 day window)

- Urine pregnancy test (if applicable)
- Medical and medications update
- Ocular pain (study eye only)
- Pin-hole VA
- Slit lamp biomicroscopy
- Ocular inflammation assessment of the anterior chamber cell and flare (study eye only)
- IOP

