12.4.3 Accountability of Study Drug

The study drug is to only be prescribed by the PI or his/her named sub Investigator(s), and is to only be used in accordance with this protocol. The study drug must only be distributed to subjects eligible under this protocol to receive study drug.

The Investigator or his/her designee must keep an accurate accounting of the study drug received from the supplier. This includes the amount of study drug dispensed to subjects, amount of study drug returned to the Investigator by the subjects, and the amount returned or disposed upon the completion of the study. A detailed inventory must be completed for the study drug.

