This SAP describes the data that will be analyzed and the subject characteristics, efficacy, and safety assessments that will be evaluated. This SAP provides details of the specific statistical methods that will be used. The statistical analysis methods presented in this document will supersede the statistical analysis methods described in the clinical protocol. If additional analyses are required to supplement the planned analyses described in this SAP, they may be completed and will be identified in the clinical study report.

2. Study Objectives

The primary objective of this study is to evaluate the efficacy and safety of OCS-01 once daily (QD) and twice daily (BID) compared to placebo (vehicle) BID in the treatment of inflammation and pain following cataract surgery.

The secondary objective of this study is to evaluate the optimal dosing frequency of OCS-01 (QD versus BID) in the treatment of inflammation and pain following cataract surgery.

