3.1 General Study Design

This study is a multi-center, randomized, double-masked, placebo (vehicle)-controlled study, designed to evaluate the efficacy and safety of OCS-01 ophthalmic suspension (QD versus BID) compared to placebo in treating inflammation and pain following cataract surgery.

Eligible subjects will be randomized [REDACTED] to receive OCS-01 QD, OCS-01 BID, or placebo BID. Subjects will dose 1 drop in the study eye BID for 14 days, beginning 1 day post-surgery in the operated eye. The study will last 20-52 days, including screening and a follow-up visit at Visit 7 (Day 22 ± 2).

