12.2 Treatment Exposure

[REDACTED]

[REDACTED]

[REDACTED]

Although not captured directly on the CRF, additional variables related to study drug administration will also be derived for summarization:

- Study drug interruption (yes/no), where interruptions will be identified via presence of a TEAE where action taken with study drug was marked as 'drug interrupted' or a protocol deviation indicating study drug was interrupted
- Premature discontinuation of study drug (yes/no), where discontinuations will be identified via presence of a TEAE where action taken with study drug was marked as 'drug withdrawn' or a protocol deviation indicating study drug was prematurely discontinued. Subjects who discontinue the study prior to Visit 6 (Day 15) will also be reviewed to verify if study drug was prematurely discontinued or not.
- Study drug completion, defined as those subjects where premature discontinuation of study drug is not equal to 'yes'

A blinded data review will be conducted prior to database lock and unblinding to identify any other cases of study drug interruption or premature discontinuation of study drug which are known to have occurred, but are not identified through the criteria above. The classifications from this final review will be used for analysis.

Subject data listings will be generated to present details of study drug assignment, study drug replacement, as well as first instillation of study medication performed in-clinic on Day 1. Details from the study drug accountability assessment will also be listed.

13. Efficacy Analyses

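### Does leaving out a by-arm dosing compliance summary undermine the QD versus BID comparison?

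*SAP*

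**What the plan says.** SAP section 2 states the aim: "The secondary objective of this study is to evaluate the optimal dosing frequency of OCS-01 (QD versus BID"). SAP 3.1 gives all arms the same drop schedule: "Subjects will dose 1 drop in the study eye BID for 14 days". Protocol 8.1.1 describes the QD arm as "OCS-01 ophthalmic suspension (QD) + Placebo (vehicle) (QD"), so one of its two daily drops is vehicle.

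Two possible sources of adherence data appear in the protocol. At Visit 2, Protocol 9.3 lists "Dose and dispense study medication and dosing diary". Protocol 12.4.3 has the site account for "the amount of study drug dispensed to subjects, amount of study drug returned to the Investigator by the subjects".

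On reporting, SAP 12.1 says that details of individual drops "done at home by subjects are not captured within the clinical database, therefore dosing compliance will not be summarized". SAP 12.2 derives three yes/no variables for summary: interruption, premature discontinuation, and "Study drug completion, defined as those subjects where premature discontinuation of study drug is not equal to" yes. The first two draw on adverse event actions and protocol deviations, supplemented by a blinded review before database lock. Early study exits are also checked for stopped drug. For returned drug, "Details from the study drug accountability assessment will also be listed".

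**The concern.** The two active arms differ only in whether one of the two daily drops contains drug. A skipped drop in the BID arm always loses drug, whereas in the QD arm it may lose only vehicle. If many drops are missed, the contrast in exposure shrinks. A similar result in the two arms could then mean either that the second active drop adds little or that it was often not taken.

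The variables in SAP 12.2 would not settle this. A subject who regularly skipped one daily drop could still count as having completed study drug, unless the lapse was recorded elsewhere. The reason given in SAP 12.1 also looks incomplete, because a percentage of doses used needs only amounts dispensed and returned, not a record of each home drop. At stake is how readers interpret the secondary objective.

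**Working it through.** The documents give no missed-dose rate and no compliance figure, so there is nothing to reproduce. The check asks how much missed drops could matter and what else limits the comparison.

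**Inputs.** Two drops daily for 14 days (SAP 3.1); one active drop daily in the QD arm and two in the BID arm (Protocol 8.1.1); cells at Visit 6, Day 15, and pain at Visit 4, Day 4 (Protocol 11.5.2); about 150 subjects (Protocol 6.1). The allocation ratio is blacked out, so 50 per arm is an assumption.

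**Planned exposure contrast.** BID gives 2 × 14 = 28 active drops and QD gives 14, a difference of 14 per subject by Day 15. At nominal Day 4, after three full dosing days, the difference is about 3 (2 to 4 over the visit window).

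**One missed differing drop.**
- BID subject, by Day 15: 1/14 = 7.1% of that subject's extra active drops. By Day 4: 1/3 = 33% (25% to 50% over the window).
- QD subject: the differing drop is vehicle, so missing it changes the active-drop contrast by nothing. Missing the QD arm's active drop widens the contrast.
- Arm level, one BID subject missing one drop: 1/(14 × 50) = 0.14% by Day 15, and 1/(3 × 50) = 0.67% by Day 4. To lose a third of the Day 4 contrast, BID subjects would have to miss one such drop each on average.

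**Widespread missed drops (illustrative rates, misses falling at random on either daily drop).** The contrast is 28 × BID adherence minus 14 × QD adherence.
- 80% in both arms: 22.4 − 11.2 = 11.2 drops.
- 90% in QD and 70% in BID: 19.6 − 12.6 = 7.0 drops.

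The second case needs adherence to differ by arm. Each arm has the same masked two-drop schedule, and nothing visible suggests why it would. These figures describe exposure, not effect on outcome.

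**Precision with full adherence.** The 95% half-width for QD minus BID is 1.96 × √(2p(1 − p)/50).
- p = 0.3 or 0.7: 1.96 × √0.0084 = 0.180.
- p = 0.5: 1.96 × √0.0100 = 0.196.

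Power for a true 10-point difference is about 17% to 18% (two-sided 5%, lower rate 30% to 50%). A small difference would be inconclusive even if every drop were taken.

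**The case for a change.** The best case for a change is that it costs little. Accountability details will be listed anyway, so a by-arm percentage of doses used might take one table. A wide confidence interval does not make adherence irrelevant either, because a larger sample would not separate a flat frequency response from an exposure contrast that was never delivered. It is also true that completion, as SAP 12.2 defines it, does not measure adherence.

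Those points stand as reasons why such a table could be useful to readers. They do not show a fault in the plan:

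- The visible protocol promises no compliance summary, so SAP 12.1 drops nothing that was planned.
- The data may not support the table. Kit contents are largely blacked out in SAP 4.2, so it is unknown whether returned drug is in countable units. The diary is dispensed, but no visible text has it collected or entered.
- Both sources can overstate adherence, and return counts cannot date a missed drop, so they would not help at Day 4.
- Adherence arises after randomization. A table would describe it but could not correct the QD-BID estimate without giving up the protection of randomization.
- Serious lapses have other routes to notice. Monitors check drug accountability (Protocol 9.9), non-compliant subjects may be withdrawn (Protocol 9.6.2), and major deviations are summarized (SAP 9) and enter the sensitivity analyses (SAP 13.1.1). The visible text does not say whether missed drops count as major.

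Protocol 12.5, on transcribing subject data into the eCRF, does not create a contradiction. It is a general statement and does not name the diary.

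**Conclusion.** No change is needed. SAP 12.1 openly accepts a limit on descriptive reporting and gives its reason. The comparison of assigned regimens remains a valid randomized comparison, and the results would be sound if the plan were followed as written. What is lost is some help in interpreting a small QD-BID difference, and that difference would already carry a half-width of about 18 to 20 points.

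This rests on an assumed 50 per arm and on the equal masked drop schedule giving no visible reason for adherence to differ by arm. The per-protocol definition, the opening of SAP 12.2 and the detail of SAP 13.1.1 are blacked out. They may already deal with missed doses, so the size of the remaining gap cannot be fixed. If the returned-drug counts prove countable, analysts can tabulate them as a supplementary analysis, which SAP section 1 allows.
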